6.1 Usual Care

All participants will be asked to continue their usual treatment, including opioid therapy management and other treatments for CLBP, through their regular providers. Usual treatment for CLBP includes: physical therapy, surgery, acupuncture, chiropractic care, hydrotherapy, medication therapy (including but not limited to: tricyclic antidepressants, selective serotonin reuptake inhibitors, serotonin and norepinephrine reuptake inhibitors, NSAIDs and other over the counter pain medication), and vitamins and herbal remedies.

In addition to study-specific outcome measures, which include self-reports on the daily opioid dose, we will also obtain data from the participant's EHR on opioids prescribed in the course of usual care; study participants will consent to the release of this medical information as a part of their consent form.

6.2 Randomization and Blinding of Study Intervention

N/A Participants will be randomized equally between MM and CBT arms (1:1 ratio), using a permuted blocks of random size strategy, stratified by site and prepared by the study statistician. Sealed envelopes with group assignment will be distributed consecutively; participants will break the seal after completing the baseline assessments.

Although participants, therapists and outcome assessors cannot be blinded to the study intervention, investigators and analysts will be blinded to the group status until the first stages of analysis and reporting are completed.

7 Study Procedures

The initial eligibility screening will take place by phone or in person (see Section 5.4.2 for details). Those eligible and interested in participation will meet in person with the study coordinator.

In-Person Consent/Enrollment/Baseline/Randomization

During the in-person meeting at baseline, eligibility will be confirmed. Eligible, interested individuals will complete the written informed consent procedures and be assigned a study ID number (approximately 20 minutes to complete, on average). Then they will complete the baseline questionnaires (approximately 55 minutes to complete, on average), followed by a brief videorecorded activity focused on the assessment of physical function (approximately 10 minutes to complete). This videorecorded activity will involve the participant performing the standardized Timed Up and Go (TUG) test, evaluating a participant ability to stand up from a chair, walk 3 meters, before walking back to the chair and sitting down,^{110,111} and a brief interview about the impact of back pain and opioid therapy, and expectations/impact of the study. Then participants will be randomized (1:1 block scheme prepared by the study statistician) to the MM or CBT groups, and receive information about details and scheduling of their respective interventions. All baseline questionnaires can be completed verbally, electronically, or on paper if the participant requests it.

Virtual Consent/Enrollment/Baseline/Randomization

During the virtual meeting at baseline, eligibility will be confirmed. Eligible, interested individuals will complete the verbal informed consent procedures and be assigned a study ID number (approximately 20 minutes to complete, on average). Then they will complete verbally or electronically the baseline questionnaires (approximately 55 minutes to complete, on average), followed by a brief videorecorded activity (approximately 9 minutes to complete), which will only involve a brief interview about the impact of back pain and opioid therapy, and expectations/impact of the study. Then participants will be randomized (1:1 block scheme prepared by the study statistician) to the MM or CBT groups, and receive information about details and scheduling of their respective interventions. All baseline questionnaires will be completed verbally, electronically, or on paper if the participant requests it.

Intervention Sessions

Participants in each intervention group will be asked to attend eight weekly 2-hour sessions of their respective intervention, practice the intervention-taught techniques at home (at least 30 minutes/day; 6 days/week during the 12-month study), and log/report their home practice. The standardized form for collecting the home practice data is attached in Appendix. Intervention sessions will be audio-recorded and monitored/audited for fidelity. In each course's final session, participants will fill out a survey (see Appendix) reflecting on their intervention- and study-related experiences. The content for both the in-person and virtual versions of the interventions is the same. They are both delivered in group format, both include a break halfway through, and both encourage active participant engagement and discussion.

In-person sessions

In-person intervention sessions will occur in a group format in a clinical, research, or community-based location. Participants will receive hard copies of the intervention materials in the first class they attend. Home practice and intervention session specific materials will be collected during the in person sessions when possible.

Virtual sessions

Virtual intervention sessions will occur in a group format using a given site's institutionally-approved HIPAA-compliant virtual video platform. Participants that do not have video capabilities will be able to call in to the sessions. Participants will receive electronic copies of the intervention materials, along with hard copies of worksheets/logs which are expected to be filled out by the participants during each session. These materials will be collected using a unique, secure link from REDCap, verbally, by phone, or per participant preference.

Follow Up Assessment Sessions (all participants regardless of study participation method)

The follow-up assessments will take place at 3, 6, 9 and 12 months after the start of a given participant's intervention. The follow-up assessments will "remotely" (online or by phone; or by participant preference) gather self-reported data at 3, 6 and 9 months (30-60 minutes to complete, on average). These assessments will also include collection of home practice minutes for the past 14 days, and side effects diaries (used to assess for any potential interval SAEs/AEs/UPs).

The final "exit" assessment at 12 months will be conducted in person or virtually. For in-person exit assessments, a participant will meet with a researcher to complete the final set of questionnaires (55 minutes to complete, on average) and the brief videorecorded activity (10 minutes to complete, on average). The virtual exit assessments will be similar to the in-person assessments, except the walking portion of the videorecorded activity will not be conducted (only the interview portion will be completed). Please see Section 9.2.3 for a summary, and Appendix for details of outcome measures.

In-depth exit interviews

In-depth exit interviews (30-45 min to complete, on average) with a subset of up to 40 participants from each arm will allow for in-depth exploration of the experience of those who reduced their daily opioid dose the most. They will be conducted by phone after the participant – in a Boston, Salt Lake or Madison site - exited the study by the qualitative methods specialists from the UW Survey Center.

Participant "check-ins"

In addition to the study contact for the intervention sessions and outcome data collection, participants will be contacted approximately every 2-4 weeks (and additionally as needed for engagement purposes) to "check in", to inquire about how the study is going for them and if they have any questions, and answer questions they may have.

Optional, Additional Testing (in-person participants only)

Participants who are eligible for it will be given the choice to consent to participate in optional, additional testing, when offered in person. The testing will be site-specific, conducted at the end of the two in-person study assessment visits (at baseline and exit). Each test will take on average approximately 15 minutes. For Madison participants, this test will involve a breath counting test using a laptop to measure mindful attention; for Boston participants, it will involve application of mechanical pressure to several body sites (pressure similar to the sensation of pressing a fingertip with steadily increasing pressure against the skin) and submerging hand in cold water at the temperature of 4 degrees centigrade (approximately the temperature of ice water) for no more than 2 minutes, to measure pain sensitivity and modulation; for Salt Lake City participants, it will involve engaging in computer-based emotional regulation and cue reactivity tasks using images from the International Affective Picture System (IAPS) and photos taken from media libraries on the internet. IAPS Images will include negative (angry faces, violent scenes), pain-related (accident scenes, injuries, medical conditions), and neutral images; opioid-related images (pills, pill bottles) will be taken from media libraries. The photographs will not be any more explicit than those seen in an R-rated movie. It is very unlikely that distress from the photos would exceed a distress which would occur on an everyday basis, given that the images we use are similar to images seen in our usual environments. Psychophysiological assessment (heart rate variability, respiration, facial activity) will be measured during these tasks.

The study manager, site managers, the PI, site-PIs and Co-Is will be responsible for monitoring and coordination of all study activities.

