the participant is not able or willing to provide data via online system, s/he will have an option to complete these surveys “on paper” or online or by phone with the assistance from the researcher. Follow-up surveys (at 3, 6, and 9-months) will be completed online and by phone, and check-ins (approximately every 2-4 weeks) will be conducted per participant communication preference. For surveys completed online, each participant will follow a unique web link (emailed to each participant at the time of follow-up) that will allow answering survey questions online. The online responses will be entered by the participant directly into the DFMCH-housed secure REDCap database using a participant-specific web link. At follow-up, those who prefer to provide data by phone will be called by the study coordinator who will mark the participant responses “on paper” or enter directly into the electronic database. Data collected “on paper” (e.g. because of participant preference; as a result of a phone interview; due to computer malfunction; data on prescribed opioids extracted from participant electronic health record) will be labeled with participant ID only, entered into the REDCap database by a research staff member and stored in a separate locked filing cabinet. Only participant ID will be linked to the participant outcome data stored in the REDCap database.

Participant videorecorded data will be uploaded to the UW DFMCH secure storage system via a web-based interface. During virtual study sessions, the videorecorded activity (interview portion) will be recorded using the institutionally-approved HIPAA-compliant virtual platform; after the session, it will be transferred to the UW DFMCH secure storage system. Security will be provided by utilizing Secure Shell (SSH) with shared/private-key encryption on all connections to and from the DFMCH storage system. Additionally, security and identify verification will be provided utilizing individual usernames and passwords (adhering to DFMCH/UW Health password complexity policy) as well as an added two-factor authentication system. This will provide an extra layer of security for access into the system. The storage system will be housed in the DFMCH server facility, which is secured 24x7 and has limited access, and will provide full-disk encryption (at rest encryption) for all files.

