Adherence to the intervention protocol will be assessed through participant session attendance of their assigned intervention (researcher-recorded); participant logs of home MM/CBT practice; and survey on non-protocol treatments.

Adverse events (AEs), Unanticipated Problems (UPs), Serious Adverse Events (SAEs), and side effects (SEs) will be evaluated at each study contact, with a *standardized UW Institute of Clinical and Translational Research's Adverse Events Tracking Log*. We will also collect data at the baseline and follow-up scheduled assessments on potential adverse effects in relation to opioid dose reduction with the 10-item brief validated instrument, the *Short Opiate Withdrawal Scale*, which assesses the presence and severity of opioid withdrawal symptoms.^{91,92}

Demographics will be collected using the NIH "minimum data set" form⁷¹ and additional questions developed by the research team and implemented in prior studies.

Qualitative measure of pain, function, and well-being will be assessed using a brief videorecorded activity of all participants at baseline and exit. It will complement quantitative measures of pain, function and QoL, and provide context

to our quantitative measurement of outcomes.^{93,94} Selected recordings will bring patient voices and experiences into view and help promote dissemination.⁹⁵ The use of a brief videorecorded activity for outcome evaluation is novel and patient-driven; it was recommended by [name], a patient advocate, and endorsed by our Patient Advisors. The premise is to enable a comparison of participant's qualitative presentation of pain, physical function and well-being (as a proxy for QoL) over time and across the two study arms, and to contrast it with the results from the validated patient-reported outcomes (PROs).

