For this activity, we will use a standardized simple functional task (for in-person meetings only) and semi-structured interview (see Appendix). The functional assessment task will be carried out by a trained researcher and utilize the Timed Up and Go (TUG) test,^{96,97} which is standardized and routinely used in clinical settings, including UW Health. TUG takes 1-3 minutes to complete and includes getting up from the chair, walking 3 meters, then coming back to sit down. The task performance will be scored, using the standardized scoring protocol developed by the research team to measure the perceived level of pain, ease of physical function, and general well-being. Following the TUG test, participants will be asked several open-ended questions about their thoughts and experience with the test, the study and the disease impact on their lives. The test administration and scoring protocol will be fine-tuned in an iterative manner, derived from the qualitative research methodological approach, based on the information from initial videorecorded activity data.

Qualitative measure of experience of those who reduced daily opioid dose the most will be assessed with in-depth exit interviews (30-45 min) with a subset of up to 40 participants from each arm (total: up to 80 participants) will allow for in-depth exploration of the experience of those who reduced their daily opioid dose the most. They will be conducted by phone after the participant exited the study by the qualitative methods specialists from the UW Survey Center. The UW Survey Center's team will help develop the protocols, conduct the interviews, and assist with data transcription, analysis and result summary. They will work with our research and stakeholder team to optimize and then continue fine-tuning the protocols in an iterative manner, derived from the qualitative research methodological approach, based on the information from initial interviews.

Optional, additional tests

These additional tests will be site-specific and only offered for in-person meetings, when in-person meetings are available. The enrolled study participants will have the choice to agree to or decline this optional testing. A separate consent will be obtained for this additional, optional testing. The additional tests (one per site) are non-invasive, and will take, on average, approximately 15 minutes to complete (see Appendix for details).

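### Section 6.2 rules out blinding for every outcome assessor, but the in-person videorecorded Timed Up and Go could be scored masked to arm and visit

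*Combined protocol and SAP*

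**What the plan says.** Protocol section 6.2 opens its blinding paragraph with "Although participants, therapists and outcome assessors cannot be blinded to the study intervention", and continues that "investigators and analysts will be blinded to the group status until the first stages of analysis and reporting are completed". No measure is excepted from the first part.

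Section 9.2.3, under Other Measures, describes a short recorded activity at baseline and exit. At in-person visits it consists of the Timed Up and Go followed by open-ended questions. On who runs it: "The functional assessment task will be carried out by a trained researcher". On scoring: "The task performance will be scored, using the standardized scoring protocol developed by the research team to measure the perceived level of pain". The same sentence adds ease of function and general well-being to what is rated. On purpose: "The use of a brief videorecorded activity for outcome evaluation is novel and patient-driven". The premise is to compare participants' presentation "over time and across the two study arms, and to contrast it with the results from the validated patient-reported outcomes".

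On storage, section 9.1 says: "Participant videorecorded data will be uploaded to the UW DFMCH secure storage system via a web-based interface". Section 7 states that virtual visits record the interview only.

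**The concern.** Participants know their arm, so self-reported outcomes cannot be masked, and 6.2 is right about those. A recorded task rated by a third party is different, because the rater need not know the arm or the visit. Pain, ease of movement and well-being as perceived by an observer are judgements, and judgements can drift with expectation. The trial hypothesises that mindfulness will do better, and some staff may share that expectation.

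The other function measures (the Oswestry index and the Brief Pain Inventory interference items) come from the unblinded participant. The recorded task is therefore the one function measure on which masked rating is possible. As written, 6.2 allows it to be scored by someone who knows both arm and visit, and nothing in 9.2.3 prevents that.

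**Working it through.** No figure in the plan depends on this point, so the check is a comparison of sections.

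1. **Is the measure used as an outcome?** Yes. Section 9.2.3 gives outcome evaluation as its use and plans a comparison over time and between arms. Section 2.2 lists functional test data among the quantitative results to be compared.

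2. **Is the scoring a judgement?** Yes, for the three rated attributes in 9.2.3. The scoring protocol is the team's own and is to be refined iteratively from early recordings, so it is not fixed at the outset.

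3. **Is the scorer or the source named?** No. Section 9.2.3 says who carries out the task and that performance is scored. It does not say by whom, when, or from what material. Sections 9.1 and 9.3 cover storage, not scoring.

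4. **Could staff know the arm?** Yes. Under section 7.2.1 the baseline meeting with the coordinator ends in randomization and scheduling. Under section 6 a second staff member or clinician is present or reachable during sessions. Under section 7.2.3 participants are contacted about every 2-4 weeks.

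5. **Which scores are exposed?**
 - *Baseline, scored on the day:* not exposed to arm, because 6.2 has the envelope opened after the baseline assessments. Exposed to visit.
 - *Baseline, scored later from the file:* exposed to both.
 - *Exit:* exposed to both.
 - *Virtual visits:* no walking task to score.

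6. **Is masking practicable?** Recordings go to one central system (9.1). The interview follows the walk (9.2.3), so a clip can stop before any talk about the study. Randomization is stratified by site (6.2), so recognising the site does not reveal the arm.

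7. **How many clips at most?** With up to 800 participants and two visits, 800 × 2 = 1,600. With 20% attrition before exit, 800 + 0.8 × 800 = 1,440. Section 9.2.3 puts the test at 1-3 minutes, so the ceiling on footage is 1,600 × 1 = 1,600 minutes (about 27 hours) to 1,600 × 3 = 4,800 minutes (80 hours). Each virtual visit lowers it.

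8. **Does it affect the sample size?** No. Section 8.1 rests on the self-reported co-primary outcomes. Its figure reproduces: a two-sample t-test with d = 0.25, two-sided alpha 0.025 and power 0.80 needs 305.4, so 306 per arm, and 306 / 0.8 = 382.5, so 383, as stated. Masked scoring leaves this unchanged.

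**The case against.** The strongest reply is that the documents do not show unmasked scoring. Section 6.2 does not name the video scorers among its outcome assessors, and it keeps investigators blinded to group. Section 2.5.2 has data coded and stripped of identifiers before investigators see them. If investigators score the recordings, masking to arm may already be intended. The detailed scoring protocol sits in an appendix that was not supplied. This stands as a reason not to allege that bias will occur. It does not settle the matter: 9.2.3 speaks only of a researcher and the research team, nothing supplied masks the visit, and the unqualified sentence in 6.2 would still need narrowing.

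A second reply is that scoring may be live, in which case 6.2 could be accurate for this measure. That is possible, and scoring from stored files is an inference that the text does not state. But live scoring at exit means that the rater knows the visit and may know the arm. The recording offers an alternative.

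Third, the measure is minor. Section 9.2.3 presents it as qualitative and complementary, and section 8.2 lists no analysis of it. Any timed element should be less open to judgement than the ratings. Both arms are active and matched for contact time, and no direction of bias can be shown. All of this stands and limits the point to an improvement.

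Fourth, masking has limits. Participants are visible on the recording, so a coded ID does not hide them from staff who know them. The documents do not show that enough uninvolved scorers exist. A strict ban on scoring by staff who had contact would therefore go too far.

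**Conclusion.** The point holds in a limited form. The blanket statement in 6.2 is broader than it needs to be: masked scoring of the in-person walking task looks achievable, and the supplied text does not provide for it. Arm-related bias can enter exit scores, and baseline scores only if they are rated after allocation. Visit-related bias can enter both. Its size and direction cannot be estimated from the documents.

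A reader might infer more, and the documents do not support it:

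- *That the primary results are at risk.* Pain, function, quality of life and opioid dose are measured by participant report and do not depend on video scoring.
- *That scoring is known to be unmasked, or known to be done from stored files.* The scorer and the source are left open.
- *That unmasked scoring would make the recordings worthless as a complement to self-report.* It would weaken an observer-rated comparison. The recordings would still give qualitative context.
- *That every recording is affected, or that masking costs nothing.* Baseline recording precedes allocation, virtual visits have no task, and clips must be prepared.

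The conclusion assumes that the walking segment can be separated from the interview, as the described order suggests, and that the unsupplied appendix does not already require masked scoring. If it does, only the wording of 6.2 needs to change.

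**What to change.** In 6.2, limit the statement that assessors cannot be blinded to measures where masking is impossible, such as participant self-report.

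In 9.2.3, state who scores the Timed Up and Go and from what material. Specify that:

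- existing scorers rate the walking segment from the stored recording;
- the clip is cut before the interview and carries none of its audio;
- clips are shown under a coded ID, in random order, with no arm or visit label;
- where feasible, a clip goes to a scorer who had no contact with that participant, for example at another site.

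The cost is modest clip preparation by existing staff: trimming, recoding and shuffling at most 1,600 short clips, fewer with attrition and virtual visits. Visits, participant burden, sample size and the planned primary and secondary analyses do not change.
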